17.4.4 Passing through the Duodenum

The duodenum and proximal jejunum are fixed. Passage through the segment is accomplished with forward rotation and gentle advancement of the scope.

Avoid prolonged rotation when the spiral segment is in the second portion of the duodenum.

Looping should be avoided but can be managed careful withdrawal of the scope along with forward rotation of the spiral segment.

[figure not shown]
Fluoroscopy or ScopeGuide may be useful in assessing looping.

Clinical Investigation Plan

CIP Reference No.:2018-GI (OEKG) -01. The **SAMISEN** study - Final Version 02 - Date 23th April 2019

17.4.5 Passing through the Small Bowel Distal to the Ligament of Treitz

[figure not shown]
Once the spiral segment is positioned in the proximal jejunum, advancement is accomplished primarily by rotation of the spiral segment.

Intermittent gentle advancement of the scope in 3-5cm increments when progress seems to slow down visually.

Insert as if drawing concentric circles.

Clinical Investigation Plan

CIP Reference No.:2018-GI (OEKG) -01. The **SAMISEN** study - Final Version 02 - Date 23th April 2019

17.4.6 Reaching the Terminal Ileum

The following images will provide indication of the scope being close to the terminal ileum.

[figure not shown]
The ileum becomes apparent with less prominent villi and prominent lymphoid follicles.

The procedure should be terminated if the cecum is encountered.

Do not pass the spiral through the ileo-cecal valve. Stop forward advancement.

[figure not shown]

Clinical Investigation Plan

[figure not shown]
CIP Reference No.:2018-GI (OEKG) -01. The **SAMISEN** study - Final Version 02 - Date 23th April 2019

17.4.7 Withdrawal Techniques

[figure not shown]
Gentle forward pressure should be maintained to facilitate a slow, controlled withdrawal. This is especially true when the duodenum is encountered.

Every effort should be made to be sure the spiral segment is free in the stomach and no longer engaged in the duodenum/ pylorus prior to allowing the spiral segment to engage the lower esophagus sphincter. This is often accomplished by intermittent use of the forward foot switch to confirm disengagement in the stomach. tent use of the forward foot switch to confirm disengagement in the stomach.

The PowerSpiral enteroscope has a special marking at 80cm to indicate the spiral segment is approaching the lower esophagus sphincter.

Clinical Investigation Plan

CIP Reference No.:2018-GI (OEKG) -01. The **SAMISEN** study - Final Version 02 - Date 23th April 2019

As the spiral segment encounters the cervical esophagus, the neck is once again extended to facilitate atraumatic withdrawal while the spiral segment is rotating.

Note

Increased resistance is an indicator of remaining pleated bowel on the spiral segment. This requires advancement of the scope holding position and then resuming backward rotation.

[figure not shown]
Clinical Investigation Plan

CIP Reference No.:2018-GI (OEKG) -01. The **SAMISEN** study - Final Version 02 - Date 23th April 2019

[figure not shown]
17.5 Retrograde Approach

17.5.1 Passing through the Colon

The spiral enteroscope can be passed through the colon with continuous rotation and gentle pressure.

Forward rotation of the spiral segment should be used for passage through the anal sphincter.

If lumen cannot be visualized, rotate with caution to advance.

CO₂ insufflation should be minimized and water injection should be considered.

[figure not shown]
[figure not shown]
Clinical Investigation Plan

CIP Reference No.:2018-GI (OEKG) -01. The **SAMISEN** study - Final Version 02 - Date 23th April 2019

17.5.2 **Eliminating a Loop**

Eliminate a loop by maintaining position of the spiral segment and withdrawing the scope while applying forward rotation to the spiral segment.

[figure not shown]
[figure not shown]
Sigmoid Colon:

Clinical Investigation Plan

CIP Reference No.:2018-GI (OEKG) -01. The **SAMISEN** study - Final Version 02 - Date 23th April 2019

Transverse Colon:

Tips

[figure not shown]
The principal is to minimize the amount of scope inserted in the colon thereby preserving as much scope length as possible with which to examine the small bowel. This is accomplished by minimizing insufflation, and the constant use of withdrawing, torquing, shortening, and pleating techniques.

Clinical Investigation Plan

CIP Reference No.:2018-GI (OEKG) -01. The **SAMISEN** study - Final Version 02 - Date 23th April 2019

17.5.3 Passing through the Ileo-cecal Valve

The ileocecal valve is intubated using standard colonoscopy techniques.

When passing through the ileocecal valve, insertion can be facilitated by decreasing the angle of insertion into the ileum by means of manual compression or postural change.

If insertion into the terminal ileum is still difficult, try retro-flexing the scope inside the cecum and inserting the U-shaped distal end of the scope into the ileum with a push-pull technique.

After passing through the ileocecal valve, advancement is accomplished by rotation of the spiral segment and intermittent advancement of the scope through the rectum as well as intermittent manual compression to facilitate acquisition of the small bowel on to the insertion tube.

[figure not shown]

Clinical Investigation Plan

CIP Reference No.:2018-GI (OEKG) -01. The **SAMISEN** study - Final Version 02 - Date 23th April 2019

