3.3.6 Sample size

A total of 260 subjects shall be enrolled into this registry. This number factors in an expected drop-out-rate of 5%. Taking into account a drop-out-rate of 5% data from a total of 245 patients is expected to be available for statistical endpoints analyses.

With a sample size of 245 patients, the SAE rate can be estimated with a precision (i.e. width of the 95% confidence interval for the SAE rate) as shown in the following table.

Clinical Investigation Plan

CIP Reference No.:2018-GI (OEKG) -01. The **SAMISEN** study - Final Version 02 - Date 23th April 2019

Table 1 Precision of estimations of the rate of patients with at least one SAE

Sample size N	Patients with SAE	Rate of patients with SAE	95% CI (Clopper- Pearson)
245	5	2.0%	0.7% - 4.7%
245	10	4.1%	2.0% - 7.4%
245	15	6.1%	3.5% - 9.9%
245	20	8.2%	5.1% - 12.3%
245	25	10.2%	6.7% - 14.7%
245	30	12.2%	8.4% - 17.0%

As historical control, a SAE rate of 8% is considered (upper limit of the accepted SAE rate for patients undergoing deep enteroscopy according to the guideline (Rondonotti et al. 2018)).

In addition, to reflect the learning curve of each individual investigator, the first 5 patients per investigator will be considered training patients to become familiar with the handling and usage. All information of these “training patients” will be documented in the eCRF. These will be analyzed separately. 12 clinical sites in Germany, Belgium, France, Netherland, Italy, Denmark, Norway and Finland will be approached. At each site there will be either one or two investigators. Based on current information there will be approx. 15 investigators participating. Adding patients from the learning curve ($15 \times 5 = 75$) and the 260 study patient’s counting towards the endpoints together this study will enroll approximately 335 patients in total.

The enrolment period starts in May/June 2019 and will stop once the expected number of patients per site is reached. This “Last-Patient-In” (end of recruitment) is expected in May/June 2020.

Each site with two investigators shall take every effort to enroll a balanced number of patients per investigator.

Statistical Analyses will be performed with SAS software version 9.4 (SAS Institute Inc., Cary, NC, USA).

Clinical Investigation Plan

CIP Reference No.:2018-GI (OEKG) -01. The **SAMISEN** study - Final Version 02 - Date 23th April 2019

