- Discontinuation of Anticoagulant therapy prior / during the procedure
- Provide information about the planned small-bowel enteroscopy
 - Main indication for the planned small- bowel enteroscopy procedure.
 - Select if a capsule endoscopy, CT/MRT enteroclysm or another imaging technique was performed previously.
 - Describe if there were any positive findings during the previous diagnostic workup (e.g. if a bleeding was detected).
- Describe the initially planned PowerSpiral approach
 - Is a total enteroscopy of the small-bowel planned?
 - Start with antegrade procedure and add a retrograde one if unsuccessful or incomplete *or*
 - Start with retrograde procedure and add an antegrade one if the initial procedure is unsuccessful or incomplete *or*
 - Perform a combined antegrade and retrograde examination during a single session.

At visit V2 and V3 (optional):

- At this visit the PowerSpiral enteroscopy will be performed.
- Enter the date and name of the responsible investigator who performs the enteroscopy.
- Enter the total procedure time (“scope-in, scope-out”) measured from initial enteroscope introduction through the bite block to final enteroscope withdrawal through the bite block (minutes) (for antegrade approach) or crossing the linea dentata of the anus in case of a retrograde approach.
- Provide information about the kind of staff and number persons needed for this enteroscopy.
- Select if an antegrade, retrograde or combined enteroscopy was performed.
- Select if a general anesthesia or sedation is used.
- Select which part of the small-bowel was reached.
- Answer if the findings of the previous imaging examinations were confirmed or not.

Clinical Investigation Plan

CIP Reference No.:2018-GI (OEKG) -01. The **SAMISEN** study - Final Version 02 - Date 23th April 2019

- Answer if there was any therapeutic intervention performed. If yes please specify in the free text section.
- Enter the time needed for any therapeutic intervention. If several slots for therapeutic interventions occurred, please add the time needed for each therapeutic slot and enter the total duration in minutes.
- Answer if any Serious Adverse Events occurred during the enteroscopy procedure.
- Document the final diagnosis after the enteroscopy
- Answer the following questions:
 - Was the therapeutic intervention successful and were all planned therapeutic aim(s) achieved?
 - Was the initial therapeutic management plan modified during the procedure?

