7 CIP DEVIATIONS

The investigator must not deviate from the procedures described in this CIP.

Under emergency circumstances, deviations from the CIP to protect the rights, safety and well-being of human subjects may proceed without prior approval of the sponsor and the EC. Such deviations must be documented and reported to the sponsor and the EC as soon as possible.

Classifications into minor and major CIP deviations will be performed by the clinical operations manager and statistician at the end of the study.

Major CIP deviations are, but are not restricted to

- Deviation from the in- and exclusion criteria

Clinical Investigation Plan

CIP Reference No.:2018-GI (OEKG) -01. The **SAMISEN** study - Final Version 02 - Date 23th April 2019

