17.5.6 Withdrawal Techniques

[figure not shown]
Slow withdrawal is accomplished with the foot switch in the reverse position and constant maneuvering of the scope tip to facilitate gradual and controlled release of the intestine off the tip of the scope.

Occasional forward activation of the spiral may be necessary for a slow, controlled withdrawal.

[figure not shown]
Once the cecum is reached, the scope is withdrawn as in a standardized colonoscopy with or without spiral rotation.

Clinical Investigation Plan

CIP Reference No.:2018-GI (OEKG) -01. The **SAMISEN** study - Final Version 02 - Date 23th April 2019

When the anal sphincter is reached, the passage is accomplished by the spiral rotation in the backward direction.

Note

Retroflexion should not be performed with the spiral segment in the patient.

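### The annex suggests retroflexion in the cecum (17.5.3), but its Note in 17.5.6, as worded, advises against retroflexion while the spiral is inside the patient

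*Protocol*

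**What the plan says.** Annex 01 of the protocol is the operator guidance for the device. Its part on the retrograde approach contains two statements on retroflexion.

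- Section 17.5.3, on passing the ileo-cecal valve, first offers compression by hand or a change of posture. It then adds: "If insertion into the terminal ileum is still difficult, try retro-flexing the scope inside the cecum", followed by feeding the bent tip into the ileum.
- Section 17.5.6, on withdrawal, ends with a Note: "Retroflexion should not be performed with the spiral segment in the patient".

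Both are current text. The list of changes in section 6 does not touch the annex. Section 7 adds a general rule: "The investigator must not deviate from the procedures described in this CIP".

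**The concern.** The first statement offers a manoeuvre as a fallback. The second cautions against the same manoeuvre under a condition that appears to be met whenever the fallback would be used. An operator who has read both sections and is having difficulty at the valve does not know which one governs.

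The device is new to the market, and each investigator's first five patients count as training cases. Perforation and mucosal damage are on the protocol's list of anticipated events in section 11.4. Guidance on a safety caution should therefore have one meaning. There is also a smaller conduct question: under section 7, the text leaves open whether a cecal retroflexion during insertion is a described procedure or a deviation.

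No effect on the serious adverse event rate is claimed, because the documents give no risk figure for retroflexion.

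**Working it through.** No formula applies to the main point. The check compares the two statements and then follows the spiral through the retrograde sequence.

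**1. The two statements**

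| | 17.5.3 | Note in 17.5.6 |
|---|---|---|
| Advice | Try retroflexion | Do not retroflex |
| Condition | Ileal entry still difficult after the first measures | Spiral inside the patient |
| Site | Cecum | None stated |
| Phase | Insertion, from the section's subject | None stated; the Note sits under withdrawal |
| Reference to the other section | None | None |

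**2. Where the spiral is when the tip is in the cecum**

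Section 17.5.3 does not say, so this is inferred from the neighbouring steps.

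- Entry (17.5.1): "Forward rotation of the spiral segment should be used for passage through the anal sphincter". The spiral enters the body at the start.
- Colon (17.5.2): "Eliminate a loop by maintaining position of the spiral segment and withdrawing the scope while applying forward rotation to the spiral segment". The sigmoid and transverse colon are then named, so the spiral is in use well before the valve.
- Beyond the valve (17.5.3): advancement relies on rotating the spiral, and no step between cecum and ileum introduces it.
- Exit (17.5.6): "When the anal sphincter is reached, the passage is accomplished by the spiral rotation in the backward direction". This follows the step in which the cecum is reached on the way out.

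The spiral is therefore inside the patient from the first passage of the anal sphincter to the last. The attempt on the valve lies between the two.

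**3. The statements combined**

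- An operator who uses the fallback follows 17.5.3 and acts against the Note as worded.
- An operator who never retroflexes complies with both, because 17.5.3 only suggests the manoeuvre.

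**4. Search for text that resolves it**

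The general guidance in 17.1 to 17.3 does not mention retroflexion, and no exception was found elsewhere in the protocol. The figures in 17.5.3 and 17.5.6 were not available for this check.

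**5. How many patients could be concerned**

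All three planned approaches in section 3.4.2 include a retrograde pass or can add one; for example, "Start with antegrade procedure and add a retrograde one if unsuccessful or incomplete". The share of patients who will have a retrograde pass is not given, nor is the frequency of difficult valve intubation. Only a wide range is possible.

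- Lower end: 0.
- Upper end at planned enrolment (section 3.3.6): 15 investigators × 5 = 75 training patients; 75 + 260 = 335. The protocol gives the same total: "this study will enroll approximately 335 patients in total".
- Upper end at the quotas in the trial summary, if all 12 sites had two investigators and filled their places: 12 × 22 = 264; 24 × 5 = 120; 264 + 120 = 384.

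The figure of 335 is thus a planning number and not a strict ceiling. Neither upper figure estimates how often the fallback would be used.

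**The case against.** The best answer is that the Note covers withdrawal only. It closes the withdrawal section, directly after the step in which the spiral leaves through the anus. The annex's other Notes concern the step they stand under, and general advice has its own sections. Advice in 17.5.3 that is specific to one site and one step could then stand beside a caution for another phase. This reading is plausible, and it may be what was intended. However, the Note sets its condition by the position of the spiral and not by phase. If withdrawal was meant, the Note has to say so.

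A second answer is that operators may not be confused in practice. Section 1.1 requires considerable experience in deep enteroscopy and documented training before the first patient. The training material and the figures might settle the matter. That cannot be excluded, but it does not repair the text.

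Third, the section 7 argument should not be pressed far. Much of the annex is written as tips, breach of the eligibility criteria is the only major deviation named (the list is open), and retroflexion is not among the data items in section 3.4.2. No consequence for the analysis populations has been shown.

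**Conclusion.** The inconsistency is real as the text stands: following 17.5.3 as written means acting against the Note in 17.5.6 as written. This rests on one inference, that the spiral is inside the patient when the tip is in the cecum, which the annex's entry, colon and exit steps support. It also assumes that the unseen figures carry no qualifying text. Confidence is medium, because a withdrawal-only intention is plausible.

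The practical size is unknown. The point concerns operator guidance alone and leaves the statistical conclusions untouched. It should be fixed because the correction is small and the text concerns a safety caution.

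**What to change.** The sponsor should reconcile 17.5.3 with the Note in 17.5.6 and leave one consistent statement on retroflexion. That statement should name the phase of the procedure or the position of the spiral to which it applies, and each section should refer to the other. Sites and trainers should then be notified, and the training material checked against the corrected page. The clinical content of the statement is for the sponsor and its clinical experts to decide.

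The cost is a corrected annex page and a notice to sites and trainers. Data collection, sample size and analysis do not change.

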17.5.4 Passing through the Small Bowel

[figure not shown]
Once the spiral segment is positioned in the terminal ileum, advancement is accomplished primarily by rotation of the spiral segment and intermittent gentle advancement of the scope in 3-5 cm increments when progress seems to slow down visually.

17.5.5 Reaching the Proximal Jejunum

The following images will provide indication of the scope being close to the proximal jejunum.

The procedure should be terminated if the ampulla or duodenal bulb is encountered.

[figure not shown]

Clinical Investigation Plan

[figure not shown]
CIP Reference No.:2018-GI (OEKG) -01. The **SAMISEN** study - Final Version 02 - Date 23th April 2019

17.5.6 Withdrawal Techniques

[figure not shown]
Slow withdrawal is accomplished with the foot switch in the reverse position and constant maneuvering of the scope tip to facilitate gradual and controlled release of the intestine off the tip of the scope.

Occasional forward activation of the spiral may be necessary for a slow, controlled withdrawal.

[figure not shown]
Once the cecum is reached, the scope is withdrawn as in a standardized colonoscopy with or without spiral rotation.

Clinical Investigation Plan

CIP Reference No.:2018-GI (OEKG) -01. The **SAMISEN** study - Final Version 02 - Date 23th April 2019

When the anal sphincter is reached, the passage is accomplished by the spiral rotation in the backward direction.

Note

Retroflexion should not be performed with the spiral segment in the patient.

1.1 Protocol Version and Amendments

The statistical analysis plan is based on final version 02 of the study protocol of study SAMISEN dated April 23rd, 2019 (CIP#: 2018-GI(OEKG) – 01).

1.2 Applicable Standards

None.

1.3 Review Report

<text>

1.4 Other Documents

[figure not shown]
None.

2 Study Design and Objectives

2.1 Study Design

This is a international, multicenter, open label, non-randomized, prospective, observational study.

2.2 Flow chart of study activities

2.3 Study Objectives

The primary endpoint of this study is the assessment of the rate of serious adverse events to show a non-inferiority to preceding generations of balloon assisted enteroscopes. Thus, the observed rate of serious adverse events will be computed alongside it's 95% Clopper-Pearson confidence interval. If the upper confidence limit will be 8% or less, non-inferiority will be concluded.

Secondary objectives are the description of the following parameters:

- Reaching the anatomical region of interest
- Therapeutic yield
- Total procedure time
- Total small bowel enteroscopy rate
- User feedback
- Safety profile
- Effect of the learning curve

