Endpoints	
 • Diagnostic Yield: Defined as the percentage of procedures that either confirmed a diagnosis from previous studies, or established a new definitive diagnosis at the anatomical location identified in previous studies or findings that could explain the clinical symptoms • Therapeutic Yield: Defined as the percentage of patients with any endoscopic intervention / therapy with the exception of biopsies • Total procedure time: (starting with oral /anal insertion until final withdrawal of the device) • Total therapeutic intervention time • Total small bowel enteroscopy rate: Defined as complete evaluation of the small bowel either with a single approach or combined anterograde and retrograde approach (if complete small bowel enteroscopy is intended anyway) • Endoscopic success rate • Safety: Incidence (% of subjects) and frequency (no. of subjects) with device or procedure related Serious Adverse Events (SAEs) and Device Deficiencies (DD) observed during/after the procedure • User feedback and assessment of handling characteristics of the device
Study Design	International, multicenter, open label, non-randomized, prospective, observational study.
Sample Size	260 subjects will be enrolled into this registry including an expected rate of 5% of losses-to-follow-up during study conduct. The first 5 procedures for each investigator will be performed to get used to the device. Data on these “learning curve” procedures will be captured and analyzed separately. The dataset for final analysis (e.g. procedure time, rate of SAEs etc.) will include 260 cases from procedure #6 onwards in order to account for a learning curve effect. The sponsor plans to activate 12 sites with one or two investigators at each site. Each site shall enroll up to 22 subjects (notwithstanding the learning curve cases) to allow for the same quota per site. Overall approximately 335 subjects will be enrolled (including cases for the learning curve).

Clinical Investigation Plan

CIP Reference No.:2018-GI (OEKG) -01. The **SAMISEN** study - Final Version 02 - Date 23th April 2019

Timelines	Study Start (Enrollment of First Patient) is planned for May/June2019. Enrollment period: 1 year (until May/June 2020). Study closure: Q2/2020.

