2 TRIAL OBJECTIVES

2.1 Objective

The main objective of this registry is to collect data on the safety and performance of the new motorized PowerSpiral device when used as intended by the manufacturer. It is assumed that the new device and its safety profile is non-inferior to preceding generations of balloon assisted enteroscopes.

As clinical performance and efficacy is equally important for the user this study also collects efficacy and handling data of the new device.

With this registry OLYMPUS complies with Post-Market Clinical Follow-up (PMCF) requirements.

Clinical Investigation Plan

CIP Reference No.:2018-GI (OEKG) -01. The **SAMISEN** study - Final Version 02 - Date 23th April 2019

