3.1.4 Replacement of Subjects

If subjects enrolled into this study withdraw their consent or drop out for other reasons before the small-bowel enteroscopy was actually performed the site shall continue to enroll subjects and conduct enteroscopies until the quota of 22 “subjects counting” for the site has been completed. Besides that, it is not foreseen to replace subjects that drop out after the first enteroscopy but before hospital discharge.

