6 AMENDMENTS TO THE CIP

CIP amendments or supplements (apart from minor administrative changes) require a written amendment. Amendments must be approved by the EC and the regulatory authorities, if locally applicable, before implementation. A copy of the written approvals will be provided to the investigators.

The following list provide an overview about the changes compare to CIP version no. 01 from 20. December 2018.

Table 3 List of changes CIP version 01 versus CIP version 02.

Amend- ment no. 01	Section	Previous version CIP version 01 from 20 th Dec 2018	Changed Version CIP version 02 from 23 April 2019
	Trial summary / endpoints	
Endpoints
 
....
 
 • Endoscopic and ERCP success rates in patients with altered upper GI anatomy (e.g. Roux-en-Y gastric bypass). 	
Endpoints
 
....
 
 • Endoscopic success rates.
	Trial summary/ study Population	
Inclusion criteria
 
 1. Signed informed consent 2. Patients with small bowel disease indicated for deep enteroscopy, including but not limited to: 
 • Gastrointestinal bleeding • Crohn's disease • Abdominal pain or chronic diarrhea • Large polyps (>10–15mm) in the jejunum and ileum in patients with Peutz–Jeghers syndrome • Nonresponsive or refractory coeliac disease • Results and hints from other preliminary investigations, e.g. small-bowel capsule endoscopy, small-bowel imaging examinations etc. which warrant further work-up with antegrade and/or retrograde enteroscopy of the small-bowel. 
or
 
 • Patients with altered upper GI anatomy (e.g. Roux-en-Y or BII) indicated for 	
Inclusion criteria
 
 1. Signed informed consent 2. Patients with small bowel disease indicated for deep enteroscopy, including but not limited to: 
 • Gastrointestinal bleeding • Crohn's disease • Abdominal pain or chronic diarrhea • Large polyps (>10–15mm) in the jejunum and ileum in patients with Peutz–Jeghers syndrome • Nonresponsive or refractory coeliac disease • Results and hints from other preliminary investigations, e.g. small-bowel capsule endoscopy, small-bowel imaging examinations etc. which warrant further work-up with antegrade and/or retrograde enteroscopy of the small-bowel.

Clinical Investigation Plan

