3.1 Populations for Analysis

All patients who did not undergo at least one enteroscopy will be considered as dropouts. Dropouts will be excluded from any statistical analyses.

Four different analysis populations will be defined:

The **core safety population (cSAF)** will consist of all patients who underwent at least one enteroscopy. Training patients will not be part of the cSAF.

The **general safety population (SAF)** will consist of all patients who underwent at least one enteroscopy including the training patients.

The **core intent-to-treat population (cITT)** will include all patients who underwent at least one enteroscopy and did not have any major protocol deviations. Training patients will not be part of the cITT.

The **general ITT population (ITT)** will comprise all patients who underwent at least one enteroscopy and did not have any major protocol deviation including the training patients.

Only patients of part A are covered by this SAP. For the analysis of data from patients of part B (ERCP patients), a separate SAP will be prepared.

The safety analysis will be performed on the safety population (SAF), which consists of all patients who underwent at least one enteroscopy.

Efficacy analyses will be based on the intent-to-treat (ITT) population, which includes all patients

- who underwent at least one enteroscopy and
- who had not major protocol deviations.

Note: Final decisions regarding validity will be made during the Review Meeting and documented in the Review Report (see Section 1.3).

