3.7 Safety Analysis

3.7.1 Primary Safety Analysis

The primary safety analysis of the serious adverse events will be based on the cSAF. The rate of serious adverse events during and after enteroscopy procedure will be computed as the number of such serious adverse events divided by the number of patients in the cSAF. A 95% Clopper-Pearson confidence interval will be computed for the rate to assess the variability of the estimate. In case of an upper 95% confidence limit von 8% or below, non-inferiority to preceding generations of balloon assisted enteroscopes will be concluded.

The primary endpoint will be assessed in the core SAF as primary analysis. As secondary analyses, the primary endpoint will be assessed for the SAF, ITT and core ITT as well as for training patients only.

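### The 8% SAE ceiling is not justified as a balloon rate or a margin, so passing the rule shows an SAE rate below 8%, not non-inferiority to balloon enteroscopes

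*SAP*

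**What the plan says.** SAP 2.3 makes the SAE rate the primary endpoint, gives its purpose as showing non-inferiority to balloon devices, and sets the rule on the 95% Clopper-Pearson interval: "If the upper confidence limit will be 8% or less, non-inferiority will be concluded". SAP 3.7.1 repeats the rule in the core safety population and states that "non-inferiority to preceding generations of balloon assisted enteroscopes will be concluded". There the rate is the number of SAEs divided by the number of patients.

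The SAP does not say where 8% comes from. The only account is in protocol 3.3.6: "As historical control, a SAE rate of 8% is considered (upper limit of the accepted SAE rate for patients undergoing deep enteroscopy", with the cited guideline given as the source. Protocol 3.2.3 makes balloon devices, as described in that same review, the historical controls, and protocol 1.2 says the SAE rate will be compared with that review's historical data. Neither section gives a figure. Protocol 2.1 treats the claim as a premise: "It is assumed that the new device and its safety profile is non-inferior to preceding generations of balloon assisted enteroscopes".

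On the number analysed, protocol 3.3.6 expects data from 245 patients, while the protocol summary says the final dataset "will include 260 cases from procedure #6 onwards in order to account for a learning curve effect". Protocol 3.1.4 adds that, after losses before the procedure, "the site shall continue to enroll subjects and conduct enteroscopies until the quota of 22" counting subjects is filled. SAP 3.1 states: "All patients who did not undergo at least one enteroscopy will be considered as dropouts". The core safety population is therefore likely to be nearer 260 than 245; both are shown below.

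**The concern.** A non-inferiority conclusion needs a comparator rate and a tolerated excess over it. The plan has one number, 8%, and it is not established as either. Protocol 3.3.6 labels it a historical control, but describes it as a limit of acceptability, and for deep enteroscopy in general rather than for balloon devices. A ceiling that a guideline accepts need not be the rate that balloon devices achieve.

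The study's main conclusion is at stake. A report that passes the rule would state a comparative safety claim against an established class of devices, and its reader could not tell how many extra SAEs per 100 patients that claim allows.

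**Working it through.** **Inputs.** Cut-off 8% and two-sided 95% Clopper-Pearson interval (SAP 2.3, 3.7.1); n = 245 (protocol 3.3.6) and n = 260 (protocol summary). The count x is patients with at least one SAE, as in protocol Table 1. The balloon rate b is not in the documents, so values of b are assumptions.

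**Step 1: the plan's own figures.** The limits are the 2.5% quantile of Beta(x, n − x + 1) and the 97.5% quantile of Beta(x + 1, n − x). At n = 245 and x = 5, 10, 15, 20, 25, 30 they give 0.67–4.70, 1.97–7.38, 3.47–9.90, 5.06–12.33, 6.71–14.69 and 8.42–17.02%. All six intervals in Table 1 reproduce.

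**Step 2: where the rule passes.**
- n = 260: x = 12 (4.6%) gives 2.41–7.92% and passes; x = 13 has an upper limit of 8.40% and fails.
- n = 245: x = 11 (4.5%) gives 2.26–7.89% and passes; x = 12 has an upper limit of 8.40% and fails.

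**Step 3: what the rule tests.** The probability of passing is P(X ≤ 12) for X ~ Bin(260, p), or P(X ≤ 11) for X ~ Bin(245, p).

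| True SAE rate p | n = 260 | n = 245 |
|---|---|---|
| 3% | 94.8% | 93.2% |
| 4% | 75.6% | 72.2% |
| 5% | 46.0% | 43.0% |
| 6% | 21.3% | 19.7% |
| 8% | 2.3% | 2.2% |

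At a true 8% the error is just under the nominal one-sided 2.5%. On patient counts this is a sound test of whether the rate is below 8%. No balloon rate enters the calculation.

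**Step 4: the margin it implies.** Implied margin = 8% − b.

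| Assumed balloon rate b | Implied margin |
|---|---|
| 8% | 0 points |
| 6% | 2 points |
| 4% | 4 points |
| 2% | 6 points |

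At b = 8% passing shows a rate below a control that is treated as known without error, and the comparative conclusion follows. At any lower b the claim carries a margin that nobody has stated or defended.

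**Step 5: the numerator.** A Clopper-Pearson interval assumes at most one count per patient, and SAP 3.7.1 counts events. Suppose 12 of 260 patients have an SAE and one of them has two. The patient count is 12 (upper limit 7.92%, pass). The event count is 13, and treating it as binomial gives 8.40%, a fail. Steps 2 and 3 therefore do not carry over to the rate as SAP 3.7.1 defines it.

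**The case against.** The best reply is that the plan does say what 8% is. The main clause of protocol 3.3.6 makes it the historical control, and the parenthesis only gives its origin. Protocol 1.2 and 3.2.3 tie the historical balloon comparison to the same review. Read together, 8% is the balloon benchmark, the margin is zero and the conclusion follows. A fixed cut-off can also be both a control and an upper limit if the source's tolerance is built into it. The design is openly single-arm against literature, so few readers would mistake the comparison for a concurrent one.

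Much of this stands. The documents lean towards the control reading, and it would be wrong to say that they contradict themselves or that 8% cannot be a balloon benchmark. But no section states a balloon SAE rate or a zero margin, and the one description of 8% is of an accepted limit for deep enteroscopy generally. What is missing is the justification, and a primary conclusion should not rest on the reader supplying it.

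A reader might go further and infer that a device with more SAEs than balloon devices would be declared non-inferior. At an assumed balloon rate of 2%, 11/245 and 12/260 do pass with lower limits (2.26% and 2.41%) above that rate. At an assumed 3% or more, no passing result at n = 245 has a lower limit above the balloon rate. Since the documents give no rate, they do not support that inference.

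**Conclusion.** The concern holds as a gap in justification. SAP 2.3 and 3.7.1 attach a comparative conclusion to a benchmark that neither document establishes as a balloon rate or as a rate plus a margin. As an accepted ceiling, 8% supports one statement: the SAE rate is below 8%. The comparative claim tolerates an excess of 8% minus an unstated rate, which is 0 to 6 points over the assumed range of 8% down to 2%.

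Two other readings go too far. One is that the rule is a faulty test: on patients with at least one SAE it is sound, and a true 8% passes about 2% of the time. The other is that it is sound as the SAP writes it: the event numerator in 3.7.1 breaks the binomial basis of the interval. Nor do the pass probabilities show that the study is too small, because the plan states no expected SAE rate or target power to judge them against.

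Confidence is high for the textual gap. The size of the consequence is unknown, because it depends on a balloon rate that the documents do not give.

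**What to change.** - **SAP 2.3 and 3.7.1:** replace the non-inferiority conclusion with a statement that the SAE rate is shown to be below the 8% performance goal. Make any comparison with published balloon rates descriptive.
- **SAP 3.7.1:** apply the rate, interval and rule to patients with at least one SAE, matching protocol Table 1. Event counts can be reported alongside.
- **Alternative:** keep the non-inferiority wording only if the plan states the balloon SAE rate, its source, and a justified margin or an explicit zero margin.
- **Protocol, at the next amendment:** align 3.3.6 (what 8% is), 2.1 (the non-inferiority assumption) and 3.2.3, which would otherwise name balloon devices as historical controls with no control figure.

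The SAP edits are a few sentences and need no new data, cut-off or sample size. The protocol edits fall under section 6: "CIP amendments or supplements (apart from minor administrative changes) require a written amendment", with ethics committee approval, so they can wait for the next amendment. The cost is a less ambitious claim than non-inferiority.
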